7.2.2. Treatment Compliance and Modifications

A given administration will be considered non-compliant if the patient did not take the planned dose of treatment as required by protocol (i.e. a syringe not fully injected is considered as a non-compliant administration). No imputation will be made for missing or incomplete data.

Percentage of compliance for a patient will be defined as the number of administrations that the patient was compliant (planned dose fully injected) divided by the total number of administrations that the patient was planned to take during each of treatment period (from the first to the last date of IMP administration within each period).

$$\text{Percentage of compliance (\%)} = \left[\frac{\text{Total number of compliant injections during specific treatment period}}{\text{Number of planned injections during specific treatment period}} \right] \times 100\%$$

Loading doses for the same patient will be counted as 1.

Percentage of compliance and percentage of injections with compliance to the IMP administration will be summarized descriptively as quantitative variables (number, mean, SD, median, Q1, Q3, minimum and maximum) separately for each treatment period (double-blind treatment period and OLE) and overall. In addition, the percentage of compliance will be presented by the specific ranges for each treatment group:

- <80%
- ≥80 % to < 120%
- ≥120%

An overdose (accidental or intentional) with the IMP is an event suspected by the Investigator or spontaneously notified by the participant and defined as at least twice the intended dose within the intended therapeutic interval, adjusted according to the tested drug. Cases of symptomatic overdoses will constitute AESIs and will be listed as such. More generally, dosing irregularities will be listed in [Section 5.2](#).

Dose modification of IMP for an individual patient is not allowed and therefore no summary of dose modifications will be provided. Drug-dispensing irregularities are included as part of the protocol deviations summary ([Section 5.2](#)).

8. Efficacy Analysis

Efficacy analyses will be performed on the mITT analysis set, OLE analysis set or PSG analysis set depending on the efficacy endpoints.

Patients will be analyzed for efficacy according to the treatment group to which they are allocated by the IRT according to the randomization schedule at the randomization visit (as randomized), irrespective of the treatment actually received.

For the analysis of primary objective in the double-blind treatment period,

- The null statistical hypothesis tested is that there is no treatment difference between dupilumab and placebo on sleep quality NRS in adult patients with moderate to severe AD and sleep disturbance.
- the alternative statistical hypothesis tested is that there is a treatment difference between dupilumab and placebo on sleep quality NRS in adult patients with moderate to severe AD and sleep disturbance.

Note that due to the small sample size in the PSG analysis set, no statistical testing will be conducted for PSG related endpoints. Summary statistics with 95% CI by treatment group will be provided.

Statistical testing will be only be conducted on results for the double-blind treatment period. Statistical testing will not be conducted for the assessments completed during OLE period. All related endpoints will be summarized.

All efficacy measurements collected during the study will be considered for analyses, including those obtained after IMP discontinuation.

All daily assessments (e.g., sleep quality NRS, actigraphy parameters, sleep diary, etc.) will be analyzed as weekly averages for the week immediately preceding the study visit.

Line plots for change from baseline or percent change from baseline will be presented by treatment group, displaying the mean, median, Q1 and Q3 at each visit. These plots will be provided for the primary and all secondary continuous endpoints.

Bar plots for percentage of patients with EASI50, EASI75 and EASI90 will be presented by treatment group, displaying the percentage of EASI responders at each visit.

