9.3 POPULATIONS FOR ANALYSES

For purposes of analysis, the following populations are defined in [Table 3](#).

Table 3 - Populations for analyses

Population	Description
Enrolled	All participants who sign the ICF.
Randomized	The randomized population includes all patients with a treatment kit number allocated and recorded in the IRT database, and regardless of whether the treatment kit was used or not. Patients treated without being randomized will not be considered randomized and will not be included in any efficacy population, but will be included in the safety population.
Intent-to-treat (ITT)	All randomized patients, and will be analyzed according to the treatment group allocated by randomization
Efficacy	The ITT Population
Safety	The safety population includes all patients who actually received at least 1 dose or partial dose of the IMP, analyzed according to the treatment actually received. Randomized patients for whom it is unclear whether the study medication was taken will be included in the safety population as randomized.

Abbreviations: ICF = informed consent form; IRT = interactive response technology; ITT = intent-to-treat

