4.3. Analysis Sets

Patients exposed to IMP before or without being randomized will not be considered randomized and will not be included in any analysis set and will be reported in listings under a treatment group named “not randomized but treated”. However, if these patients experienced any safety event, they would be documented separately in the clinical study report.

Patients randomized but not treated will be included in any efficacy analyses and will be reported in listings under a treatment group named “randomized but not treated”. These patients will be analyzed for efficacy analyses according to the treatment group to which they are allocated to by the IRT.

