4.3.3. Modified ITT (mITT) Analysis Set

The modified ITT analysis set (mITT) consists of ITT patients who had a baseline and at least one post-baseline measurement.

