15.3. Missing Efficacy Data

15.3.1. Handling of missing data and data whose interpretations have changed

The following will be applied to all efficacy endpoints:

- Patients will be encouraged to stay in the study if they discontinue the IMP, even due to Covid-19 pandemic (IcEv1 and IcEv2).
 - If discontinuation or interruption of study treatment due to Covid-19, off-treatment data will be set to missing. The assessments after patients resume treatment will be used.
 - If discontinuation or interruption of study treatment not due to Covid-19, all data collected following schedule after the treatment discontinuation will be used in the analysis.
- Taking selected prohibited medications that affect sleep (Protocol Section 6.5.1), all sleep related assessments (sleep quality NRS, SCORAD sleep VAS and total score, PROMIS sleep impairment SF8a total score, ESS, and actigraphy data) on that corresponding night will be set to missing. AD assessments will be included in the analyses.
- Taking selected prohibited medications that affect AD (Protocol Section 6.5.1), all AD assessments will be set to missing after the medication usage.
- Taking rescue medications for AD (ie. to control intolerable AD symptoms) is allowed. For the purpose of efficacy analysis, all AD assessments will be set to missing after the medication usage.
- If a patient discontinues from treatment or from the study, or is taking rescue or selected prohibited medications, the patient will be counted as a non-responder for the time points after discontinuation or rescue/prohibited medication start for all binary endpoints.

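### The SAP names three different EASI denominators (ITT, mITT, evaluable at the visit) against the protocol's ITT, and narrows the safety set; its list of changes records neither

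*SAP*

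**What the plan says.** **Efficacy set.** Protocol 9.3, Table 3 defines the efficacy population as "The ITT Population", and ITT as "All randomized patients, and will be analyzed according to the treatment group allocated by randomization". SAP Section 8 says instead that "Efficacy analyses will be performed on the mITT analysis set, OLE analysis set or PSG analysis set depending on the efficacy endpoints". Appendix 15.1 gives mITT in every row, including the primary endpoint. Under SAP 4.3.3 the mITT set "consists of ITT patients who had a baseline and at least one post-baseline measurement"; which measurement is not stated.

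Elsewhere the SAP keeps ITT. Table 3.1.2 gives ITT as the population for the primary and secondary estimands. The sample programs for the primary MMRM (8.1.1) and the EASI responder model (8.2.8) both select on the ITTFL flag. The text of 8.2.8 then bases responder percentages on patients evaluable at the visit.

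**Non-responder rule.** For binary endpoints, SAP 15.3.1 says that if a patient discontinues treatment or the study, "the patient will be counted as a non-responder for the time points after discontinuation"; the same holds after rescue or selected prohibited medication. The binary row of 15.1 also treats missing as non-response, but on mITT.

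**Safety set.** Protocol Table 3 says that patients treated without being randomised "will not be included in any efficacy population, but will be included in the safety population". SAP 4.3 says that such patients "will not be included in any analysis set and will be reported in listings", and 4.3.6 limits the safety set to randomised patients.

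**Record of changes.** SAP Section 13 lists the new PSG and OLE sets. It lists neither the use of mITT nor the narrower safety set, and the SAP document history does not list them either.

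**The concern.** A randomised patient who leaves before any post-baseline assessment is a treatment failure under 15.3.1 and is absent under mITT. A patient with no Week 12 EASI is a failure under 15.1 and may be absent under 8.2.8. Leaving failures out can raise an arm's responder rate and cannot lower it. It also shifts the treatment comparison by an amount that depends on how loss divides between the arms. EASI50 and EASI75 are protocol secondary endpoints, so the choice of denominator should not be left to the programmer.

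The safety change is a separate matter. It moves a group that the protocol placed in the safety tables to listings and narrative. Section 13 treats other population changes as reportable, so a reader would expect to find both of these there.

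**Working it through.** **1. The plan's own figure.** The plan gives no number that depends on this point. Its sample-size statement (SAP 4.1: 50 placebo, 100 dupilumab, difference 25, SD 44, two-sided 0.05) reproduces: 25 / (44 × √(1/50 + 1/100)) = 3.28, and Φ(3.28 − 1.96) = 0.907, against the stated 90%. The choice of analysis set does not enter this calculation.

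**2. MMRM endpoints.** A patient with no post-baseline value, or no baseline from which to form a change, contributes no row, and nothing is imputed (SAP 8.1.3). If mITT is read endpoint by endpoint, or as any measurement, ITT and mITT give the same fit.

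**3. EASI responders.** The passages compare as follows.

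| Source | Denominator | No post-baseline value at all | Measured earlier, no Week 12 value |
|---|---|---|---|
| Protocol Table 3 with SAP 15.3.1 | all randomised | non-responder if discontinued | non-responder if discontinued |
| SAP 15.1 | mITT, missing = non-responder | left out | non-responder |
| SAP 8.2.8 text | evaluable at the visit | left out, unless imputed patients count as evaluable | left out, same proviso |
| SAP 8.2.8 code | ITTFL | kept only if the dataset holds a non-responder record | same |

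**4. Size, under assumptions.** The documents give neither EASI response rates nor the share never measured. I assume 134 dupilumab and 67 placebo (201 split 2:1) and response of 60% v 30% among measured patients, so the mITT difference is 30.0 points. Never-measured patients count as non-responders, and losses are rounded to whole patients.

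ITT rate = (rate among measured) × (number measured) / (number randomised).

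| Never measured, dupilumab / placebo | Measured | ITT rates | ITT difference | mITT minus ITT |
|---|---|---|---|---|
| 2% / 2% | 131 / 66 | 58.7% v 29.6% | 29.1 | +0.9 |
| 5% / 5% | 127 / 64 | 56.9% v 28.7% | 28.2 | +1.8 |
| 10% / 10% | 121 / 60 | 54.2% v 26.9% | 27.3 | +2.7 |
| 6% / 2% | 126 / 66 | 56.4% v 29.6% | 26.9 | +3.1 |
| 2% / 6% | 131 / 63 | 58.7% v 28.2% | 30.4 | −0.4 |
| 5% / 15% | 127 / 57 | 56.9% v 25.5% | 31.3 | −1.3 |

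For example, in row 2: 0.60 × 127/134 − 0.30 × 64/67 = 0.569 − 0.287 = 0.282. Differences are taken before rounding. Repeating the table with 70% v 40% and 50% v 25% gives an overall range of −2.3 to +3.6 points.

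The 8.2.8 reading uses the same arithmetic with the share lacking a Week 12 value, which can be larger. As an outer case, suppose the whole 20% dropout allowance of SAP 4.1 fell equally on both arms: 0.60 × 107/134 − 0.30 × 54/67 = 0.237, against 0.300.

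**5. Safety.** Here the question is textual: included under Protocol Table 3, in no analysis set under SAP 4.3, and excluded again by 4.3.6. SAP 9.1 keeps an adverse-event listing for these patients, 9.1.9 counts their deaths, and 4.3 and 5.2 call for separate documentation or description.

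**6. Week 24.** Appendix 15.1 lists mITT for these summaries. The Week 24 paragraphs of SAP 8.2 and Section 13 specify the OLE set.

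**The case against.** A reader might infer that the SAP has replaced ITT by mITT and that early dropouts are deleted from the EASI results. The documents do not support that. Table 3.1.2 and both programs keep ITT, so deletion is one reading of an inconsistent plan. Nor does early dropout by itself remove a patient from mITT. Anyone measured once after baseline stays in, and because SAP 4.3.3 does not say which measurement counts, a single diary entry might be enough. Patients who stop early are due the Visit 9 assessments, which include EASI. SAP 15.5 lets that visit be re-allocated, with Week 1 covering days 1 to 11. Only patients with no post-baseline measurement are lost through mITT.

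The statement in SAP 4.3 that randomised but untreated patients enter efficacy analyses is also weak evidence of conflict, because mITT has no dosing requirement.

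A reader might also infer that safety data are lost. They are not: the events remain in listings, the death summary and report text, and nothing in the documents shows that any such patient exists.

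EASI50/75/90 are outside the eight-endpoint hierarchy of SAP 8.2.23, so their p-values are nominal. The planned contrast is a model-based odds ratio, with a rate difference only in the last fallback.

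All of this stands and limits the weight of the point. It does not settle which denominator applies, and it does not supply the missing entries in Section 13.

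**Conclusion.** The point holds as an unreconciled conflict within the SAP and between the SAP and the protocol. The primary result, the other MMRM endpoints and the controlled type I error are not affected. For EASI50/75/90, following Section 8, 15.1 or the text of 8.2.8 can leave out randomised patients whom the SAP's own rules score as failures.

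The true size cannot be found from the documents. With 2% to 10% of each arm never measured, the EASI difference is overstated by about 1 to 3 points. Unequal loss can push it either way, from −2.3 to +3.6 points over the rates tried. The 8.2.8 reading could matter more if many patients lack a Week 12 value. All these figures rest on assumed response and loss rates.

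The safety departure is real but confined to the safety-set tables. Both changes should be settled in the text before database lock.

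**What to change.** - In SAP Section 8 and Appendix 15.1, name ITT as the efficacy set, matching Protocol Table 3, SAP Table 3.1.2 and the programs.
- For EASI50/75/90, use all randomised patients as the denominator and count missing or discontinued as non-responder. Change the sentence on evaluable patients in 8.2.8 to match. Require a non-responder record at each affected visit, so that the ITTFL filter does what the text says.
- Restore the protocol's safety definition for treated, non-randomised patients, or record and justify the departure in Section 13. Table 4.4.1 already has a label for this group, though it is described for listings.
- Set the Week 24 row of 15.1 to the OLE set.
- Enter in Section 13 any departure from the protocol that is kept.

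The cost is SAP wording, a small dataset specification, and a safety-table column if such a patient exists. The downside is slightly lower EASI responder rates in both arms.

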8.1. Primary Efficacy Endpoint

The sleep quality scale was used to assess the quality of the participant's previous nights' sleep, collected on a 11-point scale (0 to 10) in which 0 indicated worst possible sleep while 10 the best possible sleep. The primary efficacy endpoint percentage change from baseline will be calculated based on the rescaled values where each assessment (of the average over the week preceding the study visit) will be rescaled as (10 minus the observed value) such that 0 indicated the best possible sleep and 10 indicated the worst possible sleep based on the rescaled value. This is done in order to have consistent interpretations on percent improvement between scales (e.g. Peak pruritus NRS).

Rescaled sleep quality NRS = 10 minus observed sleep quality NRS.

$$\text{Percent change from baseline (\%)} = \left[\frac{\text{Week 12 rescaled sleep NRS} - \text{rescaled sleep NRS baseline value}}{\text{rescaled sleep NRS baseline value}} \right] \times 100$$

Therefore, a negative percent change from baseline will indicate an improvement.

8.1.1. Primary Analysis

Percentage change from baseline in sleep quality NRS will be analyzed using a MMRM under the MAR framework. The MMRM model will include treatment (dupilumab, placebo), baseline value of sleep quality NRS, randomization stratum (region), visits (up to week 12), treatment by visit interaction, and baseline sleep quality NRS by visit interaction terms all as fixed effects. An unstructured correlation matrix will be used to model the within -patient errors. The Kenward-Roger approximation (**ddfm=kr**) will be used to estimate the denominator of degrees of freedom. Parameters will be estimated using restricted maximum likelihood method with the Newton-Raphson algorithm. LS mean difference between the dupilumab and placebo group, the corresponding 95% CI of the differences and 2-sided nominal p-values will be provided. The primary p-value is at Week 12. Any other p-values should be treated as suggestive for possible further study as the study is not powered for these tests.

If the number of patients in the PSG-sub study is less than 50% of planned, PSG-strata will be pooled with the non-PSG strata in the US and then there will be only 3 strata: US (combined non-PSG and PSG), Europe and ROW.

If the MMRM model fails to achieve convergence due to complexity of model specification, different covariance structures will be used according to the following order till convergence is achieved:

1. Unstructured correlation (UN)
2. Heterogeneous Toeplitz (TOEPH)
3. Homogeneous Toeplitz (TOEP)
4. First-Order Autoregressive [AR(1)]
5. Compound Symmetry (CS)

MMRM model will be built with the following sample SAS code to evaluate the treatment effect through week 12:

```
proc mixed data = adqs method = reml;
  where paramcd eq 'sleep quality NRS' and avisitn ge 2 and avisitn le 6 and ITTFL eq
  "Y";
  class usubjid stratum trt01pn avisitn;
  model pctchg = base trt01pn stratum avisitn trt01pn*avisitn base*avisitn / solution ddfm
  = kr;
  repeated avisitn / type = un subject = usubjid;
  lsmeans trt01pn*avisitn / cl;
  /*contrast "Dupilumab vs Placebo at Week 1 Visit 2"
    trt01pn -1 1 trt01pn*avisitn -1 0 0 0 0 1 0 0 0 0;
  contrast "Dupilumab vs Placebo at Week 2 Visit 3"
    trt01pn -1 1 trt01pn*avisitn 0 -1 0 0 0 0 1 0 0 0;
  contrast "Dupilumab vs Placebo at Week 4 Visit 4"
    trt01pn -1 1 trt01pn*avisitn 0 0 -1 0 0 0 0 1 0 0;
  contrast "Dupilumab vs Placebo at Week 8 Visit 5"
    trt01pn -1 1 trt01pn*avisitn 0 0 0 -1 0 0 0 0 1 0; */
  contrast "Dupilumab vs Placebo at Week 12 Visit 6"
    trt01pn -1 1 trt01pn*avisitn 0 0 0 0 -1 0 0 0 0 1;
  ods output diffs=diffs lsmeans=lsmeans;
run;
```

Note that sample code assumes the avisitn for visit 2 is 2 and avisitn for visit 6 is 6, if that is not the case, the code should be adjusted. The contrast statement assumes trt01pn for placebo is lower than that of

dupilumab. The sample contrast statement for other timepoint except week 12 is provided as well in the comment, which could be used for comparisons at other visits.

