9.2 SAMPLE SIZE DETERMINATION

The sample size calculations were based on the subset of patients who reported ≥ 5 units of baseline sleep loss and ≥ 3 units of baseline pruritus scores on the SCORAD instrument in a previous study (AD1424) evaluating efficacy of dupilumab for AD.

Since no previous data are available on daily sleep on the NRS scale, the SCORAD sleep component (VAS) data was used as a basis for the sample size determination for the primary endpoint. The variability (standard deviation) estimate for the subset of patients mentioned above was 37% for the % change from baseline to week 12. Given the uncertainty in the variability from this variable to the NRS weekly average sleep score, the above variability was inflated by ~20%, and assumed to be 44% for the primary sleep parameter. With these assumptions, a total sample of 150 (50 in placebo and 100 in dupilumab group) patients will provide 90% power (alpha = 0.05, 2-sided) to detect a treatment difference of 25% (effect size, $\Delta/\sigma = 0.57$) for the percent change from baseline.

For secondary actigraphy endpoints, sample size estimates are provided in reference to nemolizumab Ph2 data at week 4. For TST, to detect a 30 minutes difference between treatments: (2:1 allocation ratio; alpha=0.05, 2-sided), assuming the same variability at week 16 weeks as seen for nemolizumab at week 4 (=56 min), then 167 subjects are needed to provide 90% power. Furthermore, the proposed sample size would have >90% power to detect a difference of 10% for change from baseline in actigraph based sleep efficiency, assuming a variability of 11% (alpha=0.05, 2-sided). The variability estimate was based on (8) for actigraphy based sleep efficiency at week 4, inflated by 50% to account for possible increase in variability over time (from week 4 to week 16). Of note, the data used for actigraphy parameters are limited.

Allowing for drop outs, a total of approximately 201 patients will be enrolled in the study.

Considering the uncertainty of the variability of the primary endpoint, when data are available for this endpoint from about 50% of the patients, the variability will be assessed in a blinded manner, and the sample size will be re-estimated. If the re-estimated sample size is higher than the original estimate, the sample size may be increased accordingly, not to exceed a total of 150 additional patients.

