- Incidence of adverse events through week 24

Other Exploratory

- To further evaluate the effect of dupilumab on objective and subjective sleep parameters, AD-related outcomes and daytime consequences of sleep deprivation

- Percent change from baseline in sleep quality NRS to week 1, 2, 4 and 8
- Percent change from baseline in pruritus NRS to week 1, 2, 4 and 8
- Change from baseline in SE based on actigraphy to week 1, 2, 4 and 8
- Change from baseline in WASO based on actigraphy to week 1, 2, 4 and 8
- Change from baseline in TST based on actigraphy to week 1, 2, 4 and 8
- Change from baseline in SOL based on actigraphy to week 1, 2, 4 and 8
- Change from baseline in SCORAD total score and sleep VAS to week 1, 2, 4 and 8
- EASI50, EASI75 and EASI90 at weeks 1, 2, 4 and 8
- Change from baseline to week 12 in polysomnography (PSG) measures of SE, TST, WASO and SOL
- Change from baseline to weeks 1, 2, 4 and 8 in PROMIS Sleep Related Impairment SF8a total score
- Change from baseline to weeks 1, 2, 4, 8 and 12 in skin pain NRS

- Change from baseline to weeks 1, 2, 4, 8 and 12 in skin sensitivity to touch NRS
 - Change from baseline to weeks 1, 2, 4, 8 and 12 in skin burn NRS
 - Change from baseline in SOL, TST, number of awakenings, WASO, SE and how rested the participant felt when getting up at week 1, 2, 4, 8 and 12 based on sleep diary
 - Change from baseline to week 4 and 12 in Epworth Sleepiness Scale (ESS)
 - Change from baseline to week 12 in psychomotor vigilance test (PVT)
 - Change from baseline to week 12 in Running Memory, Mathematical Processing and Procedural Reaction Time scores based on the neurocognitive test (Automated Neuropsychological Assessment metrics [ANAM])
 - Work productivity and activity impairment – Atopic Dermatitis version (WPAI-AD) associated questions change from baseline to weeks 4, 8 and 12
 - Missed school/workdays from baseline to week 12
- To evaluate the relationship between sleep disturbance and other objective and subjective parameters associated with AD
 - To evaluate the effect of dupilumab in comorbid conditions
 - To evaluate the effect of dupilumab on individual quantitative and non-sleep related endpoints associated with AD at Week 24
- Relationship between variables relating to sleep disturbances (eg, TST, WASO) and objective and subjective parameters associated with AD (eg, EASI, SCORAD, pruritus NRS, DLQI, skin pain NRS, skin burn NRS and sensitivity to touch NRS)

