4.1. Sample Size

The sample size calculations were based on the subset of patients who reported ≥ 5 units of baseline sleep loss and ≥ 3 units of baseline pruritus scores on the SCORAD instrument in a previous study (AD1424) evaluating efficacy of dupilumab for AD.

Since no previous data are available on daily sleep on the NRS scale, the SCORAD sleep component (VAS) data was used as a basis for the sample size determination for the primary endpoint. The variability (standard deviation) estimate for the subset of patients mentioned above was 37% for the % change from baseline to week 12. Given the uncertainty in the variability from this variable to the NRS weekly average sleep score, the above variability was inflated by $\sim 20\%$, and assumed to be 44% for the primary sleep parameter. With these assumptions, a total sample of 150 (50 in placebo and 100 in dupilumab group) patients will provide 90% power ($\alpha = 0.05$, 2-sided) to detect a treatment difference of 25% (effect size, $\Delta/\sigma = 0.57$) for the percent change from baseline.

For secondary actigraphy endpoints, sample size estimates are provided in reference to Nemolizumab Ph2 data at week 4. For TST, to detect a 30 minutes difference between treatments: (2:1 allocation ratio; $\alpha=0.05$, 2-sided), assuming the same variability at week 16 weeks as seen for Nemolizumab at week 4 (=56 min), then 167 subjects are needed to provide 90% power. Furthermore, the proposed sample size would have $>90\%$ power to detect a difference of 10% for change from baseline in actigraphy based sleep efficiency, assuming a variability of 11% ($\alpha=0.05$, 2-sided). The variability estimate was based on for actigraphy based sleep efficiency at week 4, inflated by 50% to account for possible increase in variability over time (from week 4 to week 16). Of note, the data used for actigraphy parameters are limited.

Allowing for 20% dropouts, a total of approximately 201 patients will be enrolled in the study.

Considering the uncertainty of the variability of the primary endpoint, when data are available for this endpoint from about 50% of the patients completing Week 12, the variability will be assessed in a blinded manner, and the sample size will be re-estimated. If the re-estimated sample size is higher than the original estimate, the sample size may be increased accordingly, not to exceed a total of 150 additional patients.

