  ** 'x' should be code for the placebo group **
  model resp (event='1') = base trt01pn stratum avisitn avisitn*trt01pn base*avisitn /
    dist=binomial link=logit solution ddfm=kr;
  random _residual_ / subject=usubjid type=UN; ** type can also change here as in mixed
    to TOEPH, TOEP, AR(1) or CS to achieve convergence.**
  lsmeans trt01pn*avisitn / pdiff ilink OR CL;
run;
```

Note that sample code assumes that the relevant post-baseline visits until Week 12 are coded between 2 and 6 inclusive, if that is not the case, the code should be adjusted.

If the GLMM model fails to achieve convergence (even with simpler covariance structures), the responder variables will be analyzed using a logistic regression model, separately at each assessment time point through Week 12. The logistic regression model will include treatment (dupilumab, placebo) as fixed effect, and will include baseline value of EASI, randomization stratum (region) as fixed effect covariates. A summary table will present the estimated incidence for each treatment group and corresponding 95%

confidence interval (CI); also, the odds ratio, corresponding 95% CI and p-value for the treatment difference between the dupilumab and placebo group. An estimate of the odds ratio and a CI above 1 is an indication that you are more likely to be a responder on the active treatment group rather than placebo.

If the logistic regression model fails to achieve convergence at a post-baseline visit, the Clopper Pearson 95% CI of the incidence rate (expressed in percentage) and the 95% CI of the difference in incidence rate between treatment group and placebo (i.e. treatment – placebo) and p-value will be presented. The 95% CI for the difference between dupilumab and placebo will be based on the Cochran-Mantel-Haenszel (CMH) test adjusted by the randomization stratum, at the post-baseline time point.

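### If both the unstructured and heterogeneous Toeplitz models fail to converge, the remaining fallbacks force one variance on all visits and can understate the Week 12 standard error

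*SAP*

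**What the plan says.** SAP 8.1.1 analyses percent change in sleep quality NRS by REML with an unstructured within-patient covariance and Kenward-Roger degrees of freedom. The model covers the visits at Weeks 1, 2, 4, 8 and 12; the four earlier ones are exploratory ("Percent change from baseline in sleep quality NRS to week 1, 2, 4 and 8"). For the test that counts, "The primary p-value is at Week 12".

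If the model does not converge, "different covariance structures will be used according to the following order till convergence is achieved": (1) unstructured, (2) heterogeneous Toeplitz, (3) homogeneous Toeplitz, (4) AR(1), (5) compound symmetry. Neither the text nor the sample code names an empirical (sandwich) estimator at any step. SAP 8.1.2 plans no assumption testing.

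SAP 8.2 carries the same approach to the continuous secondary endpoints. The EASI responder code in SAP 8.2.8 starts from "random _residual_ / subject=usubjid type=UN" and its comment allows the same simpler structures.

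**The concern.** Step 2 allows a different variance at each visit. Steps 3 to 5 do not: each estimates a single variance from all five visits and applies it to the Week 12 contrast. If early changes are less spread out than late ones, the pooled value is below the true Week 12 variance, so the standard error and confidence interval are too small. Kenward-Roger adjusts for small samples, not for a wrong covariance structure, and no planned check would reveal the problem.

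At stake is the primary p-value, which under SAP 8.2.23 is also the gate to eight ordered key secondary endpoints, each tested at 0.05.

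**Working it through.** **Inputs from the documents.** Protocol 9.2: "a total sample of 150 (50 in placebo and 100 in dupilumab group) patients will provide 90% power", with the SD "assumed to be 44% for the primary sleep parameter" and a difference of 25. SAP 4.1: "Allowing for 20% dropouts, a total of approximately 201 patients will be enrolled in the study". Five post-baseline visits up to Week 12.

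**Input not given.** SDs and correlations by visit. Protocol 9.2 says there were no earlier data on the daily sleep NRS. The SD patterns below are therefore assumptions, all ending at 44.

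**Plan's own figure.** SE = 44 × √(1/50 + 1/100) = 7.62. 25/7.62 = 3.28, and 3.28 − 1.96 = 1.32, so power is 90.7% (90.3% by noncentral t). The stated 90% is reproduced.

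**Approximation with complete data.** A constant-variance structure scales the Week 12 standard error by r = pooled SD / Week 12 SD, where the pooled SD is the square root of the mean of the five variances. Two-sided type I error ≈ 2 × [1 − Φ(1.96 r)].

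| Pattern | SDs at Weeks 1, 2, 4, 8, 12 | Mean variance | Pooled SD | r | Type I error |
|---|---|---|---|---|---|
| Flat | 44, 44, 44, 44, 44 | 1936 | 44.0 | 1.000 | 5.0% |
| Mild rise | 36, 38, 40, 42, 44 | 1608 | 40.1 | 0.911 | 7.4% |
| Moderate rise | 28, 32, 36, 40, 44 | 1328 | 36.4 | 0.828 | 10.5% |
| Strong rise | 20, 25, 32, 39, 44 | 1101 | 33.2 | 0.754 | 13.9% |
| Falling | 50, 49, 48, 46, 44 | 2251 | 47.4 | 1.078 | 3.5% |

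The error reaches 10% at r = 0.839, that is, when the average variance is about 70% of the Week 12 variance (0.839² = 0.704).

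**Simulation with fitted models.** REML fits under the null, 201 patients 2:1, correlation decaying in real time over the actual weeks, and 25% monotone dropout completely at random (150/201 = 74.6% retained). There were 1,000 trials per pattern, so the Monte Carlo standard error is about 0.7 to 1.2 points. Strata were omitted, and a t reference on completers minus 3 replaced full Kenward-Roger. The falling pattern was not simulated.

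| Pattern | Unstructured | Het. Toeplitz | Toeplitz | AR(1) | Comp. symmetry |
|---|---|---|---|---|---|
| Flat | 5.6% | 4.1% | 5.4% | 5.5% | 6.1% |
| Mild | 5.5% | 4.3% | 10.3% | 9.3% | 10.0% |
| Moderate | 5.9% | 4.0% | 13.6% | 13.3% | 14.5% |
| Strong | 6.2% | 3.7% | 17.2% | 17.1% | 18.4% |

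A second run of the mild pattern (1,500 trials) gave 7.4%, 7.1% and 7.9% for the last three columns, hence the range of about 7 to 10%. A purely exponential correlation with the moderate SDs gave 3.6% for heterogeneous Toeplitz and 13.7 to 14.8% for the constant-variance structures. The simulated inflation exceeds the approximation partly because dropout leaves more early than late observations in the pooled variance. The figures may also run slightly high, since the unstructured fit itself came out at 5.5 to 6.2%.

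**What drives it.** With flat SDs and the same unequal visit spacing, Toeplitz and AR(1) stayed near 5%. Compound symmetry does not use spacing at all. The inflation comes from pooling a rising variance.

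**Sandwich errors.** In the 1,500 mild trials they brought the three structures from 7.1–7.9% to 5.3–5.7%. With flat SDs they gave 5.4–6.1%. No sandwich results are available for the moderate and strong patterns.

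**The case against.** The strongest answer is that the plan already protects itself. The order is fixed in advance, and its first fallback, heterogeneous Toeplitz, held type I error at 3.6 to 4.3% in every simulated pattern. The problem needs two failures. With five visits the unstructured matrix has 5 × 6/2 = 15 parameters for about 201 patients, so even the first failure is unlikely for the primary model. This stands, and it limits how much the point matters.

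Four stronger readings are tempting, and the documents do not support them.

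- A reader might infer that any failure of the unstructured model leads to constant variance. It leads to heterogeneous Toeplitz.
- A reader might blame unequal visit spacing. The flat-SD results show otherwise.
- A reader might take a doubling of type I error as the expected result. It needs a moderate or strong rise in SD that the documents neither give nor rule out; flat SDs cause no material inflation and falling SDs make the test conservative. The simulated rates are also not conditional on a convergence failure.
- A reader might extend the figures to every model. ACQ-5, AR-VAS, PVT and ANAM have one post-baseline visit up to Week 12, so nothing is pooled across visits. POEM, DLQI, ESS and HADS have two, where the unstructured matrix has 2 × 3/2 = 3 parameters. In the EASI responder model the binomial variance already changes with the mean; if the simpler structures fail too, SAP 8.2.8 moves to per-visit logistic regression and then CMH. EASI and the other non-key endpoints are also outside the testing hierarchy and are reported at nominal level.

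**Conclusion.** The point holds as a conditional weakness in a fallback rule. If both unstructured and heterogeneous Toeplitz fail, and if the SD rises over visits, the Week 12 test under Toeplitz, AR(1) or compound symmetry is too liberal: about 7 to 10% with a mild rise and about 10 to 18% with a moderate to strong rise, against a nominal 5%. Under flat SDs it is about 5% and under falling SDs 3.5%. These sizes rest on assumed visit SDs ending at 44; only the Week 12 value comes from the documents. The complete-data formula depends only on the ratio of SDs across visits, so the same reasoning, though not these particular values, applies to five-visit continuous key secondary endpoints. The issue is minor because the trigger is unlikely, but a fallback is written for exactly that case and the correction is cheap.

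**What to change.** In SAP 8.1.1 keep unstructured, then heterogeneous Toeplitz, and replace the last three steps with heterogeneous-variance versions, for example heterogeneous AR(1) and then heterogeneous compound symmetry. Each has 5 variances + 1 correlation = 6 parameters, fewer than the 5 + 4 = 9 of heterogeneous Toeplitz, so the list still becomes simpler step by step. Kenward-Roger stays throughout.

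If a constant-variance structure is kept as a last resort, state that empirical (sandwich) standard errors will be used for it and name the accompanying degrees-of-freedom method.

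The cost is a few lines of SAP text, to be settled before database lock, which the SAP introduction allows. The downside is confined to that last step: Kenward-Roger is given up there, and sandwich errors correct the standard error but not any bias in the estimate from a wrong covariance under dropout. Their performance with a steep rise in SD has not been shown here, which is a further reason to prefer the heterogeneous structures.
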